Effects of Radiofrequency Ablation of Posterior Nasal Nerves on Inflammatory Cytokines, Peak Nasal Inspiratory Flow, and Nasal Blood Flow in Patients with Chronic Rhinitis

NCT05648565

Version Date: 1/19/2023

Protocol Title:	Effects of Radiofrequency Ablation of Posterior Nasal Nerves on Inflammatory Cytokines, Peak Nasal Inspiratory Flow, and Nasal Blood Flow in Patients with Chronic Rhinitis
Principal Investigator:	[name]
Co-Investigators:	[name], [name], [name], [name]
Study Coordinator:	[name]
Population:	Will be enrolling at least 36 patients of good health with chronic rhinitis. Patients will be eligible for intervention if they have chronic rhinitis symptoms for at least 6 months and have failed medical treatment. Patients will be enrolled at the Texas Medical Center in Houston, Texas.
Number of Sites:	Single site / UT Houston is the only site
Study Duration:	Twelve Months
Subject Duration:	14 weeks, 28 weeks if patients decide to participate in the optional last patient visit

General Information

Patients with chronic rhinitis (CR) often fail medical management. In-office radiofrequency ablation (RFA) of the posterior nasal nerve (PNN) has been established as an effective therapy for CR. However, understanding the objective response, such as nasal patency as determined by peak nasal inspiratory flow (PNIF) and changes to type 2 cytokine profiles, to this treatment has yet to be elucidated. We will be performing RFA of the PNN and evaluating the change in PNIF, patient symptom scores and cytokine changes thereafter in patients with CR.

Background Information

CR is inflammation of the nasal mucosa that leads to symptoms such as sneezing, congestion, and post-nasal drip that is separated by an allergic response - allergic rhinitis and non-allergic rhinitis (NAR). AR is an IgE-mediated inflammation of the nasal mucosa while NAR is non-IgE-mediated and has multiple etiologies including vasomotor, hormonal, and occupational among others. Overall, the condition affects 40 million people in the US annually and is a contributor to healthcare utilization and morbidity. Research has illustrated that contributors to AR are cytokines such as Interleukin (IL-) 3, 4, 5 whom stimulate immunoglobulin production and recruit inflammatory cells such as mast cells and eosinophils. In NAR, the pathophysiology is less clear and may be associated with irregularities of neural function. Regardless, AR treatment consists of a steroid and/or antihistamine spray, saline irrigations, and antihistamines. For NAR,

anti-cholinergic sprays in addition to broad-based therapies such as steroid/antihistamine sprays are utilized. In both, there is a high rate of persistent symptoms, treatment failure, and prolonged medication administration, thus forcing patients to seek procedural interventions. Historically, options have included septoplasty, turbinate reduction, vidian neurectomy and/or posterior nasal nerve (PNN) neurectomy. However, these procedures incur risks and are typically performed in the operating room. Recently, office-based procedures have been introduced to address symptoms of nasal congestion and drainage. Temperature-controlled radiofrequency ablation (RFA) is a safe in-office procedure that has been shown to decrease symptoms. However, no data has been reported on effects of RFA on objective variables associated with rhinitis. Peak nasal inspiratory flow (PNIF) is an objective outcome for nasal congestion which is a simple, cost-effective, and reliable measure that is performed in-office. To our knowledge, PNIF has not been studied as a measure of the effectiveness of RFA of PNN. We believe that this procedure will improve nasal patency and thus PNIF. Finally, RFA of PNN has been proposed as a therapeutic option for both AR and NAR, as it has shown to be effective in all types of chronic rhinitis, possibly by changing the underlying cytokine profile in the disease. For instance, type 2 cytokines are elevated in AR and are critical in its pathophysiology. We propose that the positive symptom effects of RFA in CR patients may be linked to changes in Type 2 cytokines and we seek to measure those levels. We will then attempt to correlate or understand the relationship that these objective values have with subjective patient scores that are well established in the literature such as reflective total nasal symptom score (rTNSS) and nasal obstruction symptom evaluation (NOSE) values.

Objectives

In summary, the primary outcome of this project is to determine how RFA of the PNN affects underlying cytokine profiles in addition to peak nasal inspiratory flow levels. The secondary outcomes of this study will be to assess how RFA of the PNN changes subjective symptom scores such as rTNSS and NOSE.

Study Design

This will be a prospective, single-arm single institution study with enrollment at the Texas Sinus Institute at The University of Texas Health Science Center at Houston. The patients will be enrolled through a 12-month time frame. Each patient will have a required 14-week participation window with an optional visit at 28 weeks as well. We will be assessing the objective and subjective response of RFA of the PNN in patients with rhinitis. At each post-procedure visit including the procedure visit, we will be assessing side effects and adverse events of the treatment. The primary outcome of this project is to determine how RFA of the PNN affects underlying cytokine profiles in addition to peak nasal inspiratory flow levels, which will be determined at weeks 0 and 12 for cytokine changes and weeks 0, 4, 12 and an optional 26 weeks for PNIF. The secondary outcomes of this study will be to assess how RFA of the PNN changes subjective symptom scores such as rTNSS and NOSE and this will be assessed at weeks 0, 4, 12 and an optional 26 weeks.

Study Population

Patients between the ages of 18-80 will be eligible for intervention if they have chronic rhinitis symptoms for at least 6 months (rhinorrhea, congestion, post-nasal drip), poor response to

medical management that was attempted for at least 4 weeks, a rTNSS score ≥ 6 , as well as ≥ 2 for rhinorrhea, and ≥ 1 for congestion. Exclusion criteria consists of active sinusitis, rhinitis medicamentosa, recurrent and ongoing epistaxis, immunodeficiency as defined by an illness or a history of sinus surgery. We will perform a query within the electronic medical record to assist in finding patients with chronic rhinitis.

The following ICD-10 codes will be used:

- J30.9 Allergic Rhinitis
- J30 Vasomotor rhinitis
- R09.82 Post-nasal drip/Chronic Rhinitis
- J34.89 Rhinorrhea
- J30.81 Animal Dander rhinitis
- J30.89 Dust rhinitis
- J30.5 Food induced rhinitis
- J31 Atrophic rhinitis

Then we will reach out to them and offer them participation in the study.

Study Procedures

There will be a total of four required visits with an optional fifth visit. At the first visit, enrolled participants will be screened and stopped on all intranasal corticosteroids. The total clinic appointment should not exceed 30 minutes. At this visit, we will be obtaining all relevant demographic information for analysis such as age, gender, years of rhinitis symptoms, medical co-morbidities, types of medical management that had been trialed and for how long, history of other allergic symptoms, and specific allergic triggers or prior allergy test results. We will collect this through the electronic medical record and then collate and save this data on an encrypted hard drive. At the second visit (at least two weeks from the first visit), we will teach and train participants to perform PNIF for which we will take the highest of three repeated values, we will also collect rTNSS and NOSE values in addition to nasal secretions prior to the procedure. The patient will fill the symptom score evaluations out on handouts, and we will tabulate the responses on an encrypted drive. We will collect the PNIF values on the electronic medical record and then record and save them on an encrypted hard drive. Our laboratory has established a protocol utilizing a White Blood Cell Isolation Medium called Leukosorb (Pall Corporation, New York) for nasal secretions. The Leukosorb paper is an efficient way to collect nasal secretions for cytokine analysis. The 1 x 1 cm paper will be placed over the posterior aspect of the inferior turbinate near the treatment site under endoscopic visualization. The paper is left in place for 5 minutes and then retrieved into an Eppendorf tube on ice. The paper will be stored at -80 until processed. To process, the paper collected secretions are eluted from the Leukosorb paper by centrifugation and stored at -20C for analysis by Biolegend. For confidentiality, each patient will be assigned a study identification number and all samples collected will be labeled with a study identification number. The document key correlating patient to their study identification number will be stored in a password protected document on UT server. For the treatments, we will be using Neurent Medical's Neuromark™ system

(Neurent, Ireland). This device has been approved by the FDA for treatment of chronic rhinitis. The NEUROMARK device is an in-office, disposable bipolar RFA device with a treatment tip consisting of micro electrodes which delivers RF energy while monitoring appropriate tissue contact to maximize delivery to posterior nasal nerve and its variable branching. After topical anesthesia consisting of oxymetazoline and 1% lido followed by 4% lidocaine, the device will be placed in the posterior inferior turbinate under endoscopic visualization. The device will be activated per manufacturer's instructions. After the procedure we will allow the patient to recover appropriately and ask for any adverse events or side effects at that time. We will detail these adverse events in the electronic medical record and record them in the encrypted hard drive. The second visit should take around 45-90 minutes. There will be subsequent visits at week four post procedure and week twelve post procedure. At week four we will be assessing side effects and adverse events in addition to obtaining rTNSS, NOSE, and PNIF values. This visit should not take more than 20-30 minutes. At week 12 post-procedure we will be obtaining rTNSS, NOSE, PNIF and nasal secretions for cytokine analysis. This visit should take around 30-45 minutes at most. The last optional visit, week 26 post-procedure, will be identical to week 4's visit, and should last no more than 30 minutes. The total clinic time required will be 150 minutes with an optional extra 30 (180 minutes) should patients want to participate in the final clinic visit. After week 12, statistical analysis and comparative analytics will be initiated.

Data and Safety Monitoring

Adverse events are not expected however should they occur patients will report them to the PI of the study. Any Adverse or unanticipated events will be reviewed monthly during regularly monthly meeting involving Drs. [name], [name] and [name]. The adverse events will be adjudicated by the committee. A log of these events will be kept. Any adverse event resulting from the device will be reported to the company.

Statistics

This study will be a prospective analysis. The primary endpoint is the change in PNIF from baseline after RFN treatment of the PNN at 12 weeks. Prior literature has shown that treatment of rhinitis can lead to an increase of PNIF in variable amounts depending on baseline. Literature suggests an average increase of PNIF to be around 25-35 L/min after treatment, with a standard deviation (SD) of approximately 30 L/min. With an average expected change of 30, SD of 30, and 80% power at alpha of 0.05, the minimum sample size should be 32. Assuming a 10% dropout rate, we seek to enroll 36 eligible subjects. We will also perform analyses of rTNSS and NOSE scores. As has been published, a patient will be considered a "responder" if they have at least 30% reduction of rTNSS at 12 weeks and ≥ 1 NOSE class improvement or a reduction in NOSE at least 20% from pre-treatment. Additionally, the minimum clinically important difference (MCID) for the RQLQ(S) is established at ≥ 0.5 points and 20 for PNIF. We will be performing statistical analysis after each post-procedure visit, but the primary objective will be evaluation of the PNIF and cytokine changes after week 12. However we will also assess how PNIF scores change at weeks 4 and 26 in addition to week 12. The secondary outcomes will be to assess how RFA of the PNN changes subjective symptom scores such as rTNSS and NOSE at weeks 4, 12,

and 26. Comparative analytics will be performed on all groups. Paired t-tests, Wilcoxon-Mann t-tests, chi-squared tests and ANOVA analysis will be used. Criteria for termination of the study could be poor recruitment in which the study could not be completed within 3 years.

Ethics

We will be obtaining a waiver of consent for every patient. Each patient will have a unique identifier without any identifiable medical information. There is a risk of data breach however all information will be stored on a HIPPA compliant database on a University of Texas server that will be de-identified. The patient information will be kept using a linking log and a unique patient identifier for each patient. All data will be saved on encrypted University of Texas computers using the HIPPA compliant database. Patient information and data will be stored for three years.

Data handling and record keeping

Only collaborators of this investigation will have access to the patient data and information. We will be ensuring that all patients have a unique identifier without any medical information. All data will be saved on an encrypted hard drive and encrypted data sheets. Human subjects will not be identifiable.

Quality control and assurance

An electronic medical record will be kept for each study visit. Data documents will be compared to electronic medical record to confirm accuracy of collected data. Audits of the source data will be performed by the faculty mentor on a minimum of annual basis. Source data will be audited by at least two members of the research team after each study visit.

Publication Plan

Findings will initially be presented at American Academy of Otolaryngic Allergy conference. Thereafter, we will seek to publish our results at a high-impact, and clinically relevant, journal.

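### PNIF is first taught in the session that supplies its only pre-treatment value, so any technique gain carried to week 12 would count as treatment effect

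*Combined protocol and SAP*

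**What the plan says.** Study Procedures describes visit 1 as screening, stopping of intranasal corticosteroids and history taking, and says of it: "The total clinic appointment should not exceed 30 minutes". No PNIF is listed there. Visit 2 follows at least two weeks later and is the procedure visit. At visit 2 "we will teach and train participants to perform PNIF for which we will take the highest of three repeated values".

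Study Design schedules PNIF at "weeks 0, 4, 12 and an optional 26 weeks for PNIF". Week 0 is therefore the only value before treatment; weeks 4, 12 and 26 all come after it. The text does not spell out that the week 0 PNIF precedes the procedure, but a baseline value allows no other reading.

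The Statistics section states: "The primary endpoint is the change in PNIF from baseline after RFN treatment of the PNN at 12 weeks". The Objectives and Study Design sections name cytokine profiles as primary alongside PNIF, so PNIF is primary on either reading. On the comparator, Study Design says: "This will be a prospective, single-arm single institution study". Background Information describes PNIF as a measure "which is a simple, cost-effective, and reliable measure that is performed in-office".

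The plan contains no earlier practice session, repeat baseline, reproducibility criterion for the blows, or analysis that allows for learning.

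**The concern.** PNIF depends on a manoeuvre that the patient must be taught, and the plan itself provides for the teaching. If patients do it better at their third session than at their first, the week 12 value rises for a reason unrelated to the ablation. A control group would show the same rise and allow it to be subtracted; this design has none. The week 4 value does not help, because it is already post-treatment. None of the listed tests (paired t-tests, Wilcoxon, chi-squared, ANOVA) can split a mean change into practice and treatment.

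What is at stake is the size, and possibly the significance, of the primary result. Background Information says that, to the authors' knowledge, PNIF has not been used before to judge this procedure, so readers would have little else to set the result against.

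Here, first taught means first in this study; the plan does not address earlier experience with PNIF.

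**Working it through.** **Inputs.** From Statistics: "With an average expected change of 30, SD of 30, and 80% power at alpha of 0.05", minimum sample size 32, dropout 10%, enrolment 36, PNIF MCID 20. Assumed: a two-sided test (sidedness is not stated), zero true treatment effect, and a range of technique gains, since the documents give none.

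**The plan's own figure.** A two-group normal formula gives 2 × (1.960 + 0.842)² × (30/30)² = 15.7, so 16 per group and 32 in total. Then 32/0.90 = 35.6, so 36. Both stated figures reproduce. The match needs a two-group formula although the design is single-arm and paired; that is a separate matter, and nothing below depends on it.

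**Sensitivity of the primary test.** The plan does not say whether the SD of 30 belongs to the change or to a single visit, so two cases are used:

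- SD of change 30. This is also the value for 30 per visit with correlation 0.5: 30 × √(2 × (1 − 0.5)) = 30. SE = 30/√32 = 5.303.
- SD of change 30 × √2 = 42.43 (30 per visit, zero correlation). SE = 42.43/√32 = 7.500.

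With t(0.975, 31) = 2.0395, the smallest significant observed mean change is 2.0395 × 5.303 = 10.8 L/min or 2.0395 × 7.500 = 15.3 L/min. Both lie below the MCID of 20 and the planned change of 30.

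**Chance of p<0.05 with no treatment effect.** Noncentral t, 31 df, noncentrality = gain/SE:

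| Assumed gain (L/min) | SD of change 30 | SD of change 42.4 |
|---|---|---|
| 1 | 0.054 | 0.052 |
| 3 | 0.085 | 0.067 |
| 5 | 0.150 | 0.099 |
| 10 | 0.447 | 0.253 |
| 15 | 0.782 | 0.491 |

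Simulation with 200,000 trials per cell agrees to within 0.003.

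**Against the MCID.** The chance that the observed mean change reaches 20 is much smaller (normal approximation). For a gain of 5: (20 − 5)/5.303 = 2.83, about 0.2%, or (20 − 5)/7.500 = 2.00, about 2%. For a gain of 10: (20 − 10)/5.303 = 1.89, about 3%, or (20 − 10)/7.500 = 1.33, about 9%.

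**What earlier teaching would do.** Let successive between-session gains be g, rg and r²g.

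- Now, baseline is session 1 and week 12 is session 3. Carried gain = g + rg = g(1 + r).
- With practice at visit 1, baseline is session 2 and week 12 is session 4. Carried gain = rg + r²g = rg(1 + r), which is r times the present one.

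Take a present carried gain of 10. With r = 0.5 it falls to 5, and the chance of p<0.05 falls from 0.447 to 0.150 (SD 30) or from 0.253 to 0.099 (SD 42.4). With r = 1 it stays at 10 and nothing is gained.

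**The case against.** The strongest reply is that the hazard is hypothetical. Nothing in the documents says that PNIF improves between sessions, the plan calls the measure reliable, and it already trains patients and takes the best of three. Any effort-dependent measure in any uncontrolled study is open to the same remark. Other threats have firmer support in the text: entry requires minimum symptom scores, which invites regression to the mean, and that is just as inseparable from treatment. The larger percentages need assumed gains of 10 to 15 L/min, one third to one half of the planned effect. Against the MCID of 20, gains of 5 or 10 rarely mislead. The halving of gains is an assumption, loss of technique between visits is ignored, and spare time at visit 1 is not shown.

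Most of this stands, and it sets the level of the point. It does not remove it. Training and best of three act within a session, and the statement on reliability comes with no between-session data. The MCID comparison is correct, but the plan does not make 20 L/min a rule for success. Learning is singled out not because it is the largest single-arm threat but because an existing visit could reduce it at little cost.

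**Conclusion.** The point holds as a matter of design. The only pre-treatment PNIF comes from the session in which the study first teaches the technique, and a single-arm change to week 12 cannot distinguish a carried technique gain from a treatment effect. Each L/min of such a gain adds one L/min to the expected change; a gain of 10 would be one third of the planned 30.

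The size is unknown and may be zero. The probabilities above rest on assumed gains, 32 analysed patients, a two-sided test, zero true effect and two readings of the SD. They show what would follow if a gain existed, not that one does. The point is worth considering at lower priority, with moderate confidence.

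**What to change.** Move the first teaching of PNIF to visit 1 and add a supervised practice set there. Keep those values as training data only, since intranasal corticosteroids are only being stopped at that visit. Leave the visit 2 value, best of three before the procedure, as the baseline. Endpoint, schedule and sample size do not change.

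This lowers the bias to the extent that learning happens mainly in the first session; it does not remove it. The report should list residual learning and regression to the mean as limitations of the single-arm design.

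The cost is a few minutes at visit 1. That is our estimate, and the site should check it against the 30-minute cap. No extra visit is needed. Some patients who are never treated would be trained, and the reported PNIF gain may come out smaller.

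### The Statistics section names week-12 PNIF change as the single primary endpoint, but three other statements make cytokines primary too, with no cytokine list, alpha or any/all rule

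*Combined protocol and SAP*

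**What the plan says.** Four statements bear on what is primary.

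- **Statistics, endpoint sentence:** "The primary endpoint is the change in PNIF from baseline after RFN treatment of the PNN at 12 weeks". This is singular and tied to one time point.
- **Statistics, later in the same paragraph:** "the primary objective will be evaluation of the PNIF and cytokine changes after week 12".
- **Objectives:** the primary outcome is how the procedure "affects underlying cytokine profiles in addition to peak nasal inspiratory flow levels".
- **Study Design:** repeats the Objectives definition and adds times, "which will be determined at weeks 0 and 12 for cytokine changes". It attaches weeks 0, 4, 12 and an optional 26 to PNIF within the same primary outcome.

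The only sizing is for PNIF: "With an average expected change of 30, SD of 30, and 80% power at alpha of 0.05, the minimum sample size should be 32". That sentence also holds the only alpha in the plan. Objectives, Study Design and Statistics each list only symptom scores (rTNSS, NOSE) as secondary outcomes, so cytokines have no other place in the hierarchy.

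No analyte list is given. Background Information names type 2 cytokines as a class to be measured, and mentions IL-3, 4 and 5 only as background on allergic rhinitis. Study Procedures describes sampling and assay without naming analytes. The tests listed under Statistics are not matched to endpoints, and no multiplicity method or testing order appears.

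**The concern.** The plan carries two definitions of its primary result, and they differ on whether cytokines belong to it. Because the cytokines are also unlisted, both the choice of primary and the choice of analytes could be settled after the data are seen. In a single-arm study, prespecification is one of the few protections against selective reporting.

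The stake is how the result is reported. Suppose PNIF shows no change and one cytokine reaches nominal significance. A report written from Objectives and Study Design could call that a positive primary outcome. A report written from the endpoint sentence would have to call it a null primary. If the intention is instead that everything must succeed, error is not inflated, but nothing in the plan sizes the cytokine part. The reader cannot tell which was meant.

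**Working it through.** **1. The plan's own figure.** Inputs from Statistics: change 30, SD 30, power 80%, alpha 0.05 (sidedness not stated; two-sided assumed).

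- Two-group normal formula: n per group = 2 × SD² × (1.96 + 0.84)² / change² = 2 × 900 × 7.85 / 900 = 15.7, so 16 per group and 32 in total.
- Dropout: 32 / 0.9 = 35.6, so 36.

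Both stated numbers reproduce. The formula is a two-group one, whereas a single-arm paired test on the same inputs needs 8 (normal) or 10 (t). Here 32 is taken as given. All that this point needs is that PNIF is the only endpoint with any sizing.

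**2. What each statement implies.**

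| Place | Primary content | PNIF times |
|---|---|---|
| Statistics, endpoint sentence | PNIF only | week 12 |
| Statistics, objective sentence | PNIF and cytokines | after week 12 |
| Objectives | cytokines and PNIF | none given |
| Study Design | cytokines and PNIF | weeks 0, 4, 12, optional 26 |

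The conflict over content lies both between sections and inside Statistics. On timing, Statistics treats weeks 4 and 26 as additional, but Study Design does not separate them from week 12.

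**3. Error if any one result counted (conditional illustration).** The number of cytokine tests, k, is not in the documents, so 1, 2 and 3 are assumed. Each of m = k + 1 tests is at two-sided 0.05.

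- Independent tests: 1 − 0.95^m.
- Equal correlation ρ: 1 − ∫ φ(x) [Φ((1.96 − √ρ x)/√(1−ρ)) − Φ((−1.96 − √ρ x)/√(1−ρ))]^m dx.

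| Tests | ρ = 0 | ρ = 0.5 | ρ = 0.8 |
|---|---|---|---|
| PNIF + 1 | 9.8% | 9.1% | 7.8% |
| PNIF + 2 | 14.3% | 12.5% | 9.8% |
| PNIF + 3 | 18.5% | 15.6% | 11.4% |

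The correlations are assumed too, including the one between airflow and cytokines.

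**4. If all must succeed.** There is no inflation. The cost is power: three independent cytokines, each with an assumed 80% power, are all significant 0.8³ = 51% of the time (about 68% at correlation 0.8).

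**5. Inputs for costing the fix.** Paired t-test, 32 pairs, noncentral t.

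- Standardised change detectable with 80% power: 0.51 SD at alpha 0.05; 0.60 SD at 0.05/3 = 0.0167, which is Holm's strictest step with three cytokines.
- A gate on PNIF blocks cytokine testing with probability 1 − PNIF power at 0.05:

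| True PNIF change | SD of change 30 | SD of change 42.4 |
|---|---|---|
| 30 L/min (planned) | 0.02% | 2.8% |
| 20 (L/min inferred) | 4.5% | 26.7% |

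The 42.4 is 30 × √2. It applies only if 30 is a single-visit SD with zero correlation between baseline and week 12. Statistics attaches the SD to the average increase, so 30 as the SD of change is the more natural reading. The value 20 is the plan's minimum important difference ("points and 20 for PNIF"), which is given without a unit.

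**The case against.** The strongest reply is that the plan does name its endpoint. Only one sentence uses the word endpoint, it is singular, and the sizing follows it. The other statements are phrased as aims, so PNIF could be read as the endpoint inside a wider objective. On that reading a null PNIF result is a null primary, whatever the cytokines show. This has weight, and it rules out saying that the plan as a whole permits a cytokine-only success. It is not a full answer. Objectives and Study Design use the term primary outcome and give cytokines their own measurement times within it, and Statistics repeats the pairing.

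A reader might infer more than the documents support:

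- **That the trial's false-positive rate is 14% or 18.5%.** No rule says that any one result suffices, and the number of tests is not stated. Two cytokine tests is not even a floor, since a profile could be analysed as one composite.
- **That PNIF is underpowered.** On a paired analysis with SD of change 30, 32 pairs give more than 99% power at 30 L/min.
- **That cytokines could be tested early.** Statistics says "We will be performing statistical analysis after each post-procedure visit", while Study Procedures says "After week 12, statistical analysis and comparative analytics will be initiated". That disagreement is a separate matter. Cytokines are sampled only at weeks 0 and 12, so no cytokine change can be tested at week 4.

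It is also fair to say that being the only sized endpoint is a modest reason to prefer PNIF. On a paired analysis, 32 pairs detect about 0.51 SD for any continuous endpoint. Keeping cytokines primary is a legitimate choice if it is specified.

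**Conclusion.** The concern holds as an inconsistency in the definition of the primary, together with a missing cytokine list, alpha and decision rule. The text itself shows this; it does not depend on the arithmetic. The consequence is an open reporting choice. Its size, if any one result counted, would be about 8–10%, 10–14% or 11–18.5% for one, two or three cytokine tests instead of 5%. Those figures rest on assumed test numbers, an assumed correlation of 0.8 down to 0, and two-sided 0.05 per test, and they are not bounds.

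The point should be fixed, but the stronger label of an essential correction is not supported. The study is single-arm, states no success criterion, and needs no change to its sample size, visits or sampling.

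**What to change.** Align Objectives, Study Design and Statistics before any week-12 data are analysed.

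**Simplest option.** Name week-12 change in PNIF as the sole primary endpoint at two-sided 0.05, with weeks 4 and 26 secondary. Make week-12 change in a listed set of type 2 cytokines secondary, and state one rule:

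- (a) tested only if PNIF is significant, with Holm control at 0.05 across the listed cytokines; or
- (b) reported as estimates with confidence intervals and no confirmatory claim.

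**If cytokines stay primary.** List them and state the rule: Holm or Bonferroni across PNIF and the cytokines if any one counts, or no alpha adjustment if all must succeed. Say that no cytokine effect was sized.

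**Cost.** No patients or visits are added, and 32/36 stands.

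- The simplest option takes primary status from cytokines, which are part of the stated aim.
- Under (a), with three cytokines and 32 pairs, the worst-case detectable change rises from 0.51 to 0.60 SD before the gate is counted. The gate loss is negligible to 2.8% at the planned 30 L/min, and about 5% or 27% at 20, depending on the SD of change.
- Under (b) there is no gate, but also no confirmatory cytokine claim.
- If PNIF and three cytokines share alpha by Bonferroni (0.05/4 = 0.0125), PNIF power at 30 L/min stays at 99.8% (SD of change 30) or 90.3% (42.4). At 20 it falls from 95.5% to 86.0%, or from 73.3% to 51.4%.

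### Treated patients lost before week 12 leave the primary PNIF estimate, even those with a week-4 value, which biases a single-arm result if loss is related to response

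*Combined protocol and SAP*

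**What the plan says.** The Study Design section describes one treated group: "This will be a prospective, single-arm single institution study". The Statistics section sets the primary endpoint: "The primary endpoint is the change in PNIF from baseline after RFN treatment of the PNN at 12 weeks". Dropout appears once, after the sample size of 32: "Assuming a 10% dropout rate, we seek to enroll 36 eligible subjects".

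The methods are given as a list, with no test assigned to any endpoint: "Paired t-tests, Wilcoxon-Mann t-tests, chi-squared tests and ANOVA analysis will be used". The responder rule also rests on the week-12 visit: "a patient will be considered a 'responder' if they have at least 30% reduction of rTNSS at 12 weeks", combined with a NOSE criterion. No denominator is given for the responder rate, and no status for a patient without week-12 data.

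Under Study Procedures, the ablation is done once, at the second visit, at least two weeks after the first. PNIF, rTNSS and NOSE are taken just before it. The next visit repeats them: "At week four we will be assessing side effects and adverse events in addition to obtaining rTNSS, NOSE, and PNIF values". Nasal secretions for cytokines are taken only at weeks 0 and 12.

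**The concern.** Enrolling 36 to keep 32 protects precision. It does not protect against selective loss. A patient who leaves after the procedure has had the whole treatment and belongs in any statement of its effect, but a week-0 to week-12 change score cannot be formed for that patient. In a single-arm study there is no comparator in which similar loss might offset the bias.

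If those who leave respond differently from those who stay, the reported 12-week gain describes the stayers. The plan already schedules PNIF at week 4, so for patients who leave after that visit there is information on their early response that the week-12 estimate would not use. The responder rate has the same gap: with no denominator stated, the likely default is to divide by those who attended at week 12.

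**Working it through.** **Inputs from the Statistics section.** Mean change 30 L/min, SD 30 L/min, 80% power, alpha 0.05, 32 evaluable, 10% dropout, 36 enrolled.

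**Assumptions (not in the documents).** Changes at weeks 4 and 12 both have mean 30 and SD 30; their correlation ρ is 0.5 to 0.7; who leaves and when; 24 responders among 32 completers.

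**1. The plan's own figures.** 32/0.9 = 35.6, so 36 is right as dropout inflation, and 36 − 32 = 4 is the expected loss. The 32 itself reproduces as a two-group total: 2 × (1.96 + 0.84)² × (30/30)² = 15.7, so 16 per group and 32 in all. A paired test on the same inputs needs about 10, taking 30 as the SD of the change. That is a separate matter. Here it shows only that power is not at stake: with 32 completers, a paired t-test has power above 0.999 for a change of 30.

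**2. Which patients drop out of the estimate.** A paired t-test, a rank test on the paired changes and a standard repeated-measures ANOVA all need the week-12 value. An unpaired comparison of visits would keep leavers' earlier values, but it would compare different sets of patients and would not test the within-patient change. What is known about a leaver depends on timing:
- before the procedure: untreated, outside this point;
- between the procedure and week 4: week-0 data only;
- between weeks 4 and 12: weeks 0 and 4 for PNIF, rTNSS and NOSE; week 0 only for cytokines.

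**3. Completer mean.** Suppose the k patients with the most extreme week-4 changes among n treated leave. Then

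completer mean = 30 ± 30 × ρ × m × k/(n − k),

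where m is the average size of the k extreme standard normal values among n: 1.64 for 4 of 36 and 1.89 for 2 of 34 (by simulation).
- Lowest 4 of 36 leave: ρ = 0.5 gives 30 + 30 × 0.5 × 1.64 × 4/32 = 33.1; ρ = 0.7 gives 34.3.
- Highest 4 of 36 leave: by symmetry 26.9 and 25.7.
- Lowest 2 of 34 leave (two others having left before the procedure): 30 + 30 × 0.5 × 1.89 × 2/32 = 31.8; ρ = 0.7 gives 32.5. Simulation agrees to within 0.1 (31.7 to 32.4).
- Milder (logistic) dependence on the week-4 change, about 3.6 of 36 lost: 31.5 to 32.2.

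**4. What a likelihood method recovers.** The estimate is the completers' week-12 mean plus b × (week-4 mean of all with a week-4 value − week-4 mean of completers), where b is the completers' regression slope of week-12 change on week-4 change. In simulations of 20,000 trials:
- loss depends only on the observed week-4 change: 30.0;
- the lowest 4 on the unseen week-12 change leave: 33.6 to 35.0, against a completer mean of 36.1 to 36.2;
- the lowest 4 on week-4 change leave, but 2 of them miss week 4: about 31.5 to 32.1.

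The first result follows from the method's own assumption and does not show that the method is unbiased in general.

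**5. Responder rate with 24 responders.**
- 32 completers: 24/32 = 75%.
- 36 treated, missing as non-responders: 24/36 = 67%.
- 36 treated, all 4 missing had responded: 28/36 = 78%.
- 34 treated, missing as non-responders: 24/34 = 71%.

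**The case against.** **The method is inferred.** The plan ties no test to the primary endpoint. This stands, and it is why the point cannot rest on the paired t-test alone. It does not remove the problem, because a 12-week change needs a week-12 value under any listed test of that change.

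**Week-4 data are not wasted altogether.** The Statistics section also plans to assess PNIF change at week 4, and later leavers contribute there. True, but the week-12 estimate still loses them.

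**The size is modest.** A shift of 3 to 4 L/min is less than one standard error (30/√32 = 5.3) and well below the PNIF difference of 20 that the plan calls clinically important. This stands and limits how much weight the point should carry.

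**Stronger readings that the documents do not support.** A reader might infer that:
- the result will be overstated; but the direction depends on who leaves, and loss of the best gainers understates it;
- every leaver has a week-4 value; but those lost before that visit do not;
- all 36 will be treated; but the 10% applies to enrolment, which comes at least two weeks before the procedure;
- the mixed model restores the true value; but it does so only if loss is explained by what was observed;
- 67% is the correct responder rate; but it is a conservative bound, and 75% lies between the bounds of 67% and 78%.

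**Conclusion.** The gap is real and narrow. Dropout is handled only by enrolling 36 to leave 32, and treated patients without week 12 fall out of the primary estimate even when they have a week-4 PNIF. If loss is related to response, the estimate is biased in a direction the documents do not give.

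Under the stated assumptions, with 4 of 36 treated lost after week 4, the completer mean moves from 30 to about 33 to 34 L/min, or to about 26 to 27, according to whether the smallest or the largest gainers leave. It moves less if some of the expected losses come before the procedure. The correlation, the loss mechanism and the responder count are all assumptions. That the responder rate would be computed on completers is inferred from the plan's silence. Power is not threatened. This is a cheap improvement to the plan, not a flaw that invalidates the study.

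**What to change.** In the Statistics section:
- Define the analysis set as all patients who receive the ablation.
- Estimate the week-12 PNIF change with a mixed model for repeated measures on weeks 0, 4 and 12 with unstructured covariance, and keep the paired test on completers as a sensitivity analysis.
- Report the week-12 responder rate over all treated patients, counting missing as non-response, beside the completer rate, and label the former a conservative bound.
- Report how many patients leave before the procedure, before week 4, and between weeks 4 and 12.

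The cost is a few sentences and one extra model, with no new visits or patients. There are three downsides. The model assumes missing at random, so some bias remains if loss depends on unseen outcomes or happens before week 4. It does not help the cytokine analysis, which has no week-4 sample and remains a completer analysis. The responder figure over all treated patients will look slightly less favourable. The set and the rule should be fixed before any data are analysed, since the plan foresees analysis after each post-procedure visit.
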